6.3 Laboratory Test Result Abnormalities

The following laboratory test result abnormalities should be captured on the nonserious AE CRF page or SAE Report Form (paper or electronic) as appropriate:

- Any laboratory test result that is clinically significant or meets the definition of an SAE
- Any laboratory test result abnormality that required the subject to have study drug discontinued or interrupted
- Any laboratory test result abnormality that required the subject to receive specific corrective therapy.

It is expected that wherever possible, the clinical rather than laboratory term would be used by the reporting investigator (eg, anemia versus low hemoglobin value).

6.4 Pregnancy

If, following initiation of the study drug, it is subsequently discovered that a study subject is pregnant or may have been pregnant at the time of study exposure, including during at least 5 half-lives after product administration, the investigator must immediately notify the BMS Medical Monitor/designee of this event and complete and forward a Pregnancy Surveillance Form to BMS Designee within 24 hours and in accordance with SAE reporting procedures described in [Section 6.1.1](#).

In most cases, the study drug will be permanently discontinued in an appropriate manner (eg, dose tapering if necessary for subject safety).

In the rare event that the benefit of continuing study drug is thought to outweigh the risk, after consultation with BMS, the pregnant subject may continue study drug after a thorough discussion of benefits and risk with the subject

If the study will also include women who are NOT of childbearing potential, include the following paragraph. Otherwise, please delete the next paragraph only.

Protocol-required procedures for study discontinuation and follow-up must be performed on the subject unless contraindicated by pregnancy (eg, x-ray studies). Other appropriate pregnancy follow-up procedures should be considered if indicated.

The investigator must immediately notify the BMS (or designee) Medical Monitor of this event and complete and forward a Pregnancy Surveillance Form to BMS (or designee) within 24 hours and in accordance with SAE reporting procedures described in [Section 6.1.1](#).

Follow-up information regarding the course of the pregnancy, including perinatal and neonatal outcome and, where applicable, offspring information must be reported on the Pregnancy Surveillance Form.

Any pregnancy that occurs in a female partner of a male study participant should be reported to BMS. Information on this pregnancy will be collected on the Pregnancy Surveillance Form.

6.5 Overdose

An overdose is defined as the accidental or intentional administration of any dose of a product that is considered both excessive and medically important. Overdoses meeting the regulatory definition of an SAE will be reported as SAEs (see [Section 6.1.1](#) for reporting details).

6.6 Potential Drug Induced Liver Injury (DILI)

Specific criteria for identifying potential DILI have not been identified for this protocol. Standard medical practice in identifying and monitoring hepatic issues should be followed.

Wherever possible, timely confirmation of initial liver-related laboratory abnormalities should occur prior to the reporting of a potential DILI event. All occurrences of potential DILIs, meeting the defined criteria, must be reported as SAEs (see [Section 6.1.1](#) for reporting details).

Potential drug induced liver injury is defined as:

- 1) ALT or AST elevation > 3 times upper limit of normal (ULN)
AND
- 2) Total bilirubin > 2 times ULN, without initial findings of cholestasis (elevated serum alkaline phosphatase),
AND
- 3) No other immediately apparent possible causes of AT elevation and hyperbilirubinemia, including, but not limited to, viral hepatitis, pre-existing chronic or acute liver disease, or the administration of other drug(s) known to be hepatotoxic.

6.7 Other Safety Considerations

Any significant worsening noted during interim or final physical examinations, electrocardiogram, x-ray filming, any other potential safety assessment required or not required by protocol should also be recorded as a nonserious or serious AE, as appropriate, and reported accordingly.

7 DATA MONITORING COMMITTEE AND OTHER EXTERNAL COMMITTEES

A Data Monitoring Committee (DMC) will be established to provide oversight of safety and efficacy considerations in protocol CA209274. Additionally, the DMC will provide advice to the sponsor regarding actions the committee deems necessary for the continuing protection of subjects enrolled in the study. The DMC will be charged with assessing such actions in light of an acceptable benefit/risk profile for nivolumab. The DMC will act in an advisory capacity to BMS and will monitor subject safety and evaluate the available efficacy data for the study. Details regarding the responsibilities of the DMC including frequency of meetings will be included in the DMC charter. The oncology therapeutic area of BMS has primary responsibility for design and conduct of the study.

When required adjudicated events will be submitted to the DMC and Health Authorities for review on a specified timeframe in accordance with the adjudication documentation.

8 STATISTICAL CONSIDERATIONS

8.1 Sample Size Determination

The sample size for this study is based on a comparison of the DFS distribution between subjects randomized to receive nivolumab and subjects randomized to receive placebo. There will be two co-primary comparisons: in subjects with PD-L1 expression level $\geq 1\%$ and in all randomized subjects with an alpha allocation of 2.5% (two-sided) each.

The prevalence of subjects with PD-L1 expression level $\geq 1\%$ is expected to be around 42% (Section 1.1.4.6) and see Section 3.1 for information around anticipated number of subjects.

In time-to-events trials, the number of events and power may typically be calculated assuming an exponential distribution in each treatment arm. However for DFS, a meaningful number of long-term disease-free survivors may be observed. As a consequence, the DFS curves may not follow an exponential decay and a flattening of the curves may be observed toward the end of the tail (Section 1.1.4.9). Consequently, an exponential cure rate distribution was used to calculate the sample size.

The exponential cure rate distribution can be described with following formula:

$$S(t) = p + (1 - p) * \{e^{-\alpha t}\},$$

where p is the cure rate and α is the parameter of the exponential distribution for the non-cured population.

Based on historical data, median DFS distribution in the control arm is assumed to be 12 months with a 5 year DFS rate of 32% used as the cure rate¹ (ie, $p=0.32$ and $\alpha=0.11$). It is also assumed that DFS distribution in control arm does not depend on the PD-L1 expression level. Cure rates in subjects with PD-L1 expression level $\geq 1\%$ and in the all randomized population for the experimental arm are targeted to be 54% and 47% respectively while non cured population is assumed to follow same distribution as in the control arm. It is assumed that the effect of nivolumab vs. placebo will be delayed. A study of nivolumab vs. ipilimumab in metastatic melanoma (CheckMate 238⁵¹) suggested a 3-month delayed effect for nivolumab, therefore the model used for the experimental arm also assumes a 3-month delayed effect in subjects with PD-L1 expression level $\geq 1\%$ and in the all randomized population for the experimental arm.

Approximately 700 subjects will be randomized in 1:1 ratio to nivolumab arm and control arm respectively.

- Approximately 410 DFS events in all randomized subjects will provide around 87% power to detect an average HR of 0.72 with an overall type I error of 2.5% (two-sided)
- Approximately 162 DFS events in subjects with PD-L1 expression level $\geq 1\%$ (~294 subjects) will provide around 80% power to detect an average HR of 0.61 with an overall type I error of 2.5% (two-sided).

The target average hazard ratios were obtained via simulation using above modeling.

It is expected that the required number of events in each population will be reached when all subjects will have at least a minimum of 17 months of follow-up.

An interim DFS analysis will also be performed when 85% of DFS events in each population will be observed (ie, 348 and 137 DFS events in all randomized and in subjects with PD-L1 expression level $\geq 1\%$, respectively). The alpha level for DFS will be adjusted for the planned interim analysis using Lan-DeMets alpha spending function with the O'Brien-Fleming type of boundary in East v6.

Assuming an average accrual rate of 16 subjects per month, the accrual will take approximately 43 months. The total duration of the study from start of randomization to final analysis of DFS is

expected to be 60 months (43 months of accrual + 17 months of follow-up). DFS analyses in all randomized population and in subjects with PD-L1 expression level $\geq 1\%$ are projected to occur 45 months after start of the study for the interim analyses and 60 months (43 months of accrual + 17 months of follow-up) for the final analyses (Table 8.1-1 and Table 8.1-2).

It is expected that interim DFS analysis in each population will occur at the same time. However, because the DFS event rate pattern may be different between all randomized population and subjects with PD-L1 expression level $\geq 1\%$, the interim DFS analysis of each population might also occur separately.

Table 8.1-1: Schedule of Analyses of Primary Endpoint in all randomized population

	Interim DFS analysis	Final DFS analyses
Conditions	When 348 events of DFS are observed in all randomized subjects	When 410 events of DFS are observed in all randomized subjects
Population	All randomized subjects	All randomized subjects
Expected timing	45 months	60 months (43 months of accrual + 17 months of follow-up)
Nominal significance level/Power	0.01349149	0.02108499 / 87%
Lower boundary for statistical significance	Observed hazard ratio of 0.76	Observed hazard ratio of 0.79

Table 8.1-2: Schedule of Analyses of Primary Endpoint in subjects with PD-L1 expression level $\geq 1\%$

	Interim DFS analysis	Final DFS analyses
Conditions	When 137 events of DFS are observed in subjects with PD-L1 expression level $\geq 1\%$	When 162 events of DFS are observed in subjects with PD-L1 expression level $\geq 1\%$
Population(s)	Subjects with PD-L1 expression level $\geq 1\%$	Subjects with PD-L1 expression level $\geq 1\%$
Expected timing	45 months	60 months (43 months of accrual + 17 months of follow-up)
Nominal significance level / Power	0.01349149	0.02108499 / 80%
Lower boundary for statistical significance	Observed hazard ratio of 0.65	Observed hazard ratio of 0.69

Key secondary endpoint of OS will be formally compared (in subjects with PD-L1 expression level $\geq 1\%$ and all randomized subjects) using a hierarchical procedure in each population (see [Section 8.5](#)).

8.2 Populations for Analyses

- Enrolled subjects: All subjects who signed an informed consent form and were registered into the IVRS.
- Randomized subjects: All enrolled subjects who were randomized. This dataset will be used for baseline demographics and efficacy analyses
- Randomized subjects with PD-L1 expression level \geq 1%: All randomized subjects with baseline tumor sample testing per IHC result \geq 1% membranous staining in tumor cell. This dataset will be used for baseline demographics and efficacy analyses.
- Treated subjects: All randomized subjects who received at least one dose of study drug. This dataset will be used for safety analyses.
- Treated subjects with PD-L1 expression level \geq 1%: Randomized subjects with PD-L1 expression level \geq 1% who received at least one dose of study drug. This dataset will be used for safety analyses.

[REDACTED]

[REDACTED]

[REDACTED]

8.3 Endpoints

8.3.1 Primary Endpoint(s)

The primary endpoint of DFS will be programmatically determined based on the disease recurrence date provided by the investigator and is defined as the time between the date of randomization and the date of first recurrence as defined in [section 5.4.1](#) (local urothelial tract, local non-urothelial tract or distant) or death (of any cause), whichever occurs first. (Note: a subject who dies without reported recurrence will be considered to have recurred on the date of death.) For subjects who remain alive and whose disease has not recurred, DFS will be censored on the date of last evaluable disease assessment.

Detailed censoring rules for the primary definition of DFS are presented in Table 8.3.1-1. Sensitivity analyses of DFS will be described in the statistical analysis plan

Table 8.3.1-1: Censoring scheme used in primary definition of DFS

Situation	Date of Progression or Censoring	Outcome
Disease at baseline	Date of randomization	Event
Any recurrence (ie local urothelial tract, local non urothelial tract or distant)	Date of first recurrence	Event
Death from any cause without recurrence	Date of death	Event
No baseline disease assessment	Date of randomization	Censored

Table 8.3.1-1: Censoring scheme used in primary definition of DFS

Situation	Date of Progression or Censoring	Outcome
No on-study disease assessments and no death	Date of randomization	Censored
No recurrence and no death	Date of last evaluable disease assessment	Censored
New anticancer therapy, tumor directed radiotherapy, or tumor directed surgery received without recurrence reported prior to or on the same day*	Date of last evaluable disease assessment prior to or on the same date of initiation of subsequent therapy	Censored
Second non-urothelial primary cancer reported without recurrence reported prior to or on the same day	Date of last evaluable disease assessment prior to or on the same date of diagnosis of second non-urothelial primary cancer	Censored

*Further details regarding the censoring scheme will be provided in the statistical analysis plan.

Disease assessments will occur as below:

- Non-cystoscopy tumor imaging assessments will occur every 12 weeks from the date of first dose to Week 96 (ie, Week 12, 24, 36, 48, 60, 72, 84, 96; +/- 1 week), then every 16 weeks from Week 96 to Week 160 (i.e. Week 112, 128, 144, 160; +/- 2 weeks), then every 24 weeks until non-urothelial tract recurrence or treatment is discontinued (whichever occurs later) for a maximum of 5 years (ie, Week 184, 208, 232, 256; +/- 4 weeks).
- Non-cystoscopy tumor imaging assessments: CT of chest, and CT or MRI of abdomen, pelvis, upper urinary tract, and all known sites of disease. Use same imaging method as was used at screening/baseline.
- Cystoscopy in subjects with upper GU primaries who still have bladder intact will occur in addition to other tumor imaging assessments every 12 weeks from the date of first dose to Week 48 (ie, Week 12, 24, 36, 48 +/- 1 week), then every 24 weeks from Week 48 to Week 96 (ie, Week 72, 96; +/- 2 weeks), then every 48 weeks until non-urothelial tract recurrence or treatment is discontinued (whichever occurs later) for a maximum of 5 years (ie, Week 144, 192, 240; +/- 4 weeks).

This endpoint will be analyzed in two different populations (co-primary): Subjects with PD-L1 expression level $\geq 1\%$ and all randomized subjects.

8.3.2 Secondary Endpoints

8.3.2.1 Overall Survival (OS)

The key second secondary endpoint of Overall Survival (OS) is defined as the time between the date of randomization and the date of death (of any cause). For subjects without documentation of death, OS will be censored on the last date the subject was known to be alive. OS will be followed continuously while subjects are on the study drug and every 3 months via in-person or phone contact after subjects discontinue the study drug.

This endpoint will be analyzed in two different populations (co-primary): Subjects with PD-L1 expression level $\geq 1\%$ and all randomized subjects.

8.3.2.2 Non-Urothelial Tract Recurrence Free-Survival (NUTRFS)

The secondary endpoint NUTRFS is defined as the time between the date of randomization and the date of first local non urothelial tract or distant recurrence or death (of any cause), whichever occurs first. For subjects who remain alive and local non urothelial tract or distant recurrence-free, NUTRFS will be censored on the date of last evaluable disease assessment.

Detailed censoring rules for the primary definition of NUTRFS are presented in Table 8.3.2.2-1.

Table 8.3.2.2-1: Censoring scheme used in primary definition of NUTRFS

Situation	Date of Progression or Censoring	Outcome
Disease at baseline	Date of randomization	Event
Non-Urothelial Recurrence (ie local non-urothelial recurrence or distant metastasis)	Date of first recurrence	Event
Death from any cause without recurrence	Date of death	Event
No baseline disease assessment	Date of randomization	Censored
No on-study disease assessments and no death	Date of randomization	Censored
No recurrence and no death	Date of last evaluable disease assessment	Censored
New anticancer therapy, tumor directed radiotherapy, or tumor directed surgery received without recurrence reported prior to or on the same day *	Date of last evaluable disease assessment prior to or on the same date of initiation of subsequent therapy	Censored
Second non-urothelial primary cancer reported without recurrence reported prior to or on the same day	Date of last evaluable disease assessment prior to or on the same date of diagnosis of second non-urothelial primary cancer	Censored

*Further details regarding the censoring scheme will be provided in the statistical analysis plan.

Disease assessments as stated in [Section 8.3.1](#).

This endpoint will be analyzed in two different populations (co-primary): Subjects with PD-L1 expression level $\geq 1\%$ and all randomized subjects.

8.3.2.3 Disease Specific Survival (DSS)

The secondary endpoint DSS is defined as the time between the date of randomization and the date of death due to disease (urothelial cancer). For subjects without documentation of death, DSS will be censored on the last date the subject was known to be alive. DSS will be followed continuously as part of OS follow-up while subjects are on the study drug and every 3 months via in-person or phone contact after subjects discontinue the study drug.

This endpoint will be analyzed in two different populations (co-primary): Subjects with PD-L1 expression level $\geq 1\%$ and all randomized subjects.

[REDACTED]

[REDACTED]

[REDACTED]

[REDACTED]

[REDACTED]

[REDACTED]

[REDACTED]

[REDACTED]

[REDACTED]

[REDACTED]

8.4 Analyses

8.4.1 Demographics and Baseline Characteristics

Demographic and baseline laboratory results will be summarized by treatment arm as randomized using descriptive statistics. Analysis will be conducted on subjects with PD-L1 expression level $\geq 1\%$ and repeated on the all randomized subjects.

8.4.2 Efficacy Analyses

8.4.2.1 Primary Endpoint Methods

DFS distribution in all randomized subjects and subjects with PD-L1 expression level $\geq 1\%$ will be compared between treatment group using a two-sided stratified log-rank test at the overall significance level of 2.5% (two-sided) each.

The HR and corresponding two-sided 100x (1-adjusted α)% confidence intervals (CIs) will be estimated in a Cox proportional hazards model using treatment as a single covariate, stratified by PD-L1 status (only in the all randomized population comparison), prior neo-adjuvant cisplatin chemotherapy, positive lymph node status.

DFS curves will be estimated using the KM product-limit method. Median DFS and the corresponding two-sided 95% CIs using the log-log transformation will be computed. In addition, DFS rate at 6 months, 1 year and 2 years (and yearly after depending on the follow-up) and the corresponding two-sided 95% CIs using the log-log transformation will be computed.

Similar descriptive analyses will also be performed in subjects with PD-L1 expression level < 1%.

The assumption of proportional hazards in the Cox regression model will be examined and additional parametric models will be further investigated in case of non-proportionality.

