3.3.1 Inclusion Criteria

1) Signed Written Informed Consent

- a) Subjects must have signed and dated an IRB/IEC approved written informed consent form in accordance with regulatory and institutional guidelines. This must be obtained before the performance of any protocol related procedures that are not part of normal subject care.
- b) Subjects must be willing and able to comply with scheduled visits, treatment schedule, laboratory tests, tumor biopsies, and other requirements of the study.

2) Target Population

- a) All subjects must be status post radical surgical resection (R0) for IUC, performed within 120 days prior to randomization. Subjects with carcinoma in situ in surgical margins are not eligible for study entry.
- b) All subjects must have pathologic evidence of urothelial carcinoma (originating in bladder, ureter, or renal pelvis) at high risk of recurrence based on pathologic staging of radical surgery tissue as described in one of the two below scenarios (i or ii):
 - i) Subjects who have not received neo-adjuvant cisplatin chemotherapy: pT3-pT4a or pN+ and are not eligible for or refusing adjuvant cisplatin chemotherapy
 - (1).Subjects ineligible for adjuvant cisplatin due to any of the following criteria:⁵⁰
 - a. Creatinine Clearance (using the Cockcroft-Gault formula): < 60 mL/min
 - b. Common Terminology Criteria for Adverse Events (CTCAE) version 4, grade 2 or above audiometric hearing loss
 - c. CTCAE version 4, grade 2 peripheral neuropathy
 - d. Eastern Cooperative Oncology Group Performance Scale (ECOG PS) 2
 - e. NYHA Class III or IV Heart Failure
 - (2).Subjects that are eligible for cisplatin may be candidates if they refuse available adjuvant chemotherapy, despite being informed by the investigator about the treatment options. The subject's refusal must be thoroughly documented.
 - ii) Subjects who received neo-adjuvant cisplatin chemotherapy: ypT2-pT4a or ypN+
- c) Dominant component of histology needs to be urothelial carcinoma or transitional cell carcinoma. Foci of varied histologies (eg, minor variants) are accepted.
- d) All subjects must have disease-free status defined as no clinical or radiographic evidence of recurrence of disease documented by a complete physical examination and imaging

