## **7.5 Efficacy**

Analyses in this section will be tabulated by treatment group as randomized, unless otherwise specified.

Unless otherwise specified, efficacy analyses will be performed independently for:

- all randomized subjects
- all randomized subjects with PD-L1 expression  $\geq 1\%$ .

Unless stated otherwise, whenever a stratified analysis is specified, the following stratifications factors (recorded at randomization as per IRT) will be used:

- Receipt of neo-adjuvant cisplatin based chemotherapy for IUC (Yes vs. No)
- Pathologic status of disease in lymph nodes (N+ vs. N0/x with < 10 Nodes Removed vs. N0 with  $\geq 10$  Nodes Removed)

Only for analysis in all randomized subjects:

- PD-L1 expression level ( $\geq 1\%$  vs.  $< 1\%$ /indeterminate)

For assessing the first secondary objective (with overall survival as secondary endpoint) of this study, a hierarchical testing procedure will be used so that the overall experiment-wise Type I error rate is two-sided 0.05.

Confidence intervals (CI) for primary and secondary endpoints analyses included in hierarchy will be based on nominal significance level adjusted for primary endpoints and interim analyses to preserve overall type one error rate.

Alpha ( $\alpha$ ) for the CI will be the same as nominal significance level for hypothesis testing. CIs for other endpoints will be at the two-sided 95% level. All p-values reported will be two-sided. P-values will be rounded to the fourth decimal place. Point estimates and confidence bounds for efficacy variables will be rounded to the second decimal place.

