#### **7.5.1.1 Analysis of Disease-Free Survival**

In case of formal comparison (interim or final), DFS will be compared between the treatment groups via stratified log-rank test in the appropriate co-primary population at an overall two-sided  $\alpha = 0.025$  level for each co-primary population. The stratification factors are summarized in the [section 7.5](#).

An O'Brien and Fleming  $\alpha$ -spending function will be employed to determine the nominal significance levels for the interim and final analyses. The estimate of the DFS hazard ratio between treatment groups will be calculated using a stratified Cox proportional hazards model, with treatment as the sole covariate. Ties will be handled using the exact method. A two-sided (1-adjusted  $\alpha$ )% CI (adjusted for interim) for the hazard ratio will also be presented.

The DFS function for each treatment group will be estimated using the KM product limit method and will be displayed graphically. A two-sided 95% CI for median DFS in each treatment group will be computed via the log-log transformation method. DFS rates at fixed time points (e.g. 6 months, depending on the minimum follow-up) will be presented along with their associated 95% CIs. These estimates will be derived from the Kaplan Meier estimate and corresponding CIs will be derived based on Greenwood formula for variance derivation and on log-log transformation applied on the survivor function.

The primary definition of DFS adjusting for subsequent anticancer therapy will be used in this analysis. The two-sided log-rank p-value will be reported.

The source of DFS event (recurrence or death) will be summarized by treatment group. The status of subjects who are censored (as per primary definition of DFS) in the DFS KM analysis will be tabulated for each treatment group including the following categories:

- On-study (on-treatment, in follow-up)
- Off-study (lost to follow-up, withdraw consent, never treated)
- No baseline disease assessment
- No on-study disease assessment and no death
- Received subsequent anticancer therapy
- New non-urothelial carcinoma primary cancer

A by-subject listing will be presented including treatment group, DFS duration under the primary definition, whether the subject was censored under the primary definition, and if censored, the reason.

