### **7.5.1.2 Supportive Analyses of Disease-Free Survival**

The following sensitivity analyses will be conducted using the primary and secondary definition of DFS:

- 1) DFS using stratification factors as obtained from the baseline CRF pages (instead of IRT). The hazard ratio associated with treatment will be presented along with the associated two-sided 95% CIs. This analysis will be performed only if at least one stratification variable/factor at randomization (as per IRT) and baseline are not concordant for at least 10% of the randomized subjects.
- 2) DFS using an unstratified log rank test. The hazard ratio associated with treatment will be presented along with the associated two-sided 95% CIs.
- 3) A multivariate Cox regression model will be used in order to estimate the treatment effect after adjustment for possible imbalances in known or potential prognostic factors. The factors used in the randomization, which, by definition, will be balanced across treatment groups, will still be included in the model as stratification factors. However, all additional factors will be incorporated as covariates. The additional factors, which are all measured at baseline, will include:
  - Age (< 65 vs. ≥ 65 year)
  - Gender (Male vs. Female)
  - Baseline ECOG status (0 vs. 1 vs. 2)
  - Pathological status (pT0-2 vs. pT3 vs. pT4)

The level of the covariate normally associated with the worst prognosis will be coded as the reference level. The hazard ratio associated with treatment and with each of the baseline covariates will be presented along with associated 95% CIs.

- 4) DFS for subjects with no relevant protocol deviations. This analysis will be conducted only if there are more than 10% subjects with relevant protocol deviations. The hazard ratio associated with treatment will be presented along with the associated two-sided 95% CIs.
- 5) DFS accounting for missing disease assessments prior to DFS event (recurrence or death). This analysis will be performed only if at least 10% of DFS events (in the population of interest) have two or more missing prior disease assessment (no protocol specified disease assessment imaging completed at the expected timepoint). It will apply the following restriction to the primary definition in case a subject has two or more missing disease assessments, the subject will be censored at the last disease assessment date prior to DFS event.

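### The primary DFS analysis leaves out pT category, a collected factor that the SAP itself treats as prognostic; the planned test is valid, but adding pT as a covariate is a cheap gain of about 0 to 4 points of power

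*Protocol*

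**What the plan says.** Protocol 8.4.2.1 compares DFS in each co-primary population with a "two-sided stratified log-rank test at the overall significance level of 2.5% (two-sided) each". The hazard ratio comes from a "Cox proportional hazards model using treatment as a single covariate, stratified by PD-L1 status" (all randomized only), prior neo-adjuvant cisplatin and nodal status. SAP 7.5.1.1 agrees: the hazard ratio is "calculated using a stratified Cox proportional hazards model, with treatment as the sole covariate". SAP 7.5 fixes the strata as the randomization factors recorded in the IRT.

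pT category is neither a randomization factor (Protocol 4.4, SAP 2.2) nor a term in the primary model. Yet Protocol 3.3.1 admits subjects "at high risk of recurrence based on pathologic staging of radical surgery tissue", which means by pT or by nodal involvement. SAP 7.3.2 tabulates pathologic stage from the CRF. SAP 7.5.1.2 item 3 adds "Pathological status (pT0-2 vs. pT3 vs. pT4") to a supportive Cox model, with age, sex and ECOG status, as a known or potential predictor of outcome. SAP 7.5.1.3 makes pT a DFS subgroup. SAP 7.5.2.1 and 7.5.2.2 follow the same pattern for OS.

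**The concern.** Leaving a prognostic baseline factor out of a time-to-event analysis pulls the hazard ratio toward 1 and costs some power. A chance difference between arms in that factor also stays in the primary p-value and estimate. Here the factor is already collected, already coded in three levels for another model, and named as prognostic by the SAP. The supportive model can show what adjustment would have done, but it cannot change the result that carries alpha. If the adjusted and unadjusted results fell on different sides of the boundary, only the unadjusted one would count. The smaller PD-L1 >=1% population (about 294 subjects, 147 per arm) is the more exposed to chance imbalance.

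**Working it through.** **1. The plan's own power.** Protocol 8.1 states: "Approximately 410 DFS events in all randomized subjects will provide around 87% power to detect an average HR of 0.72"; and 80% power for 162 events and HR 0.61. Each is at two-sided 2.5%, so the critical value is 2.2414. The Schoenfeld formula is power = Φ(|ln HR| × √D / 2 − 2.2414).

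- All randomized: 0.3285 × √410 / 2 = 3.326; 3.326 − 2.241 = 1.084; power 86.1%.
- PD-L1 >=1%: 0.4943 × √162 / 2 = 3.146; 3.146 − 2.241 = 0.904; power 81.7%.

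With the interim look at the stated nominal levels these become 85.4% and 80.9%. All are within 2 points of the plan, which used simulation from a cure model. The stated power does not depend on pT adjustment.

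**2. Power with pT as a covariate.** The pT mix and the pT effect are not in the documents and are assumed throughout. There were three sets of simulations, each with one look at two-sided 2.5%. Each fitted the analysis without pT and the analysis with pT to the same data.

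- Set A: the plan's control curve S(t) = 0.32 + 0.68·exp(−0.11t), plateau 0.47 or 0.54 on nivolumab after a 3-month delay, accrual 700/16 = 43.75 months, cutoff at month 60. pT mix 25/55/20%, and no effect of other factors. 6,000 trials per cell.
- Set B: same pT mix, cure-type baseline without the delay, a nodal effect and strata included, analysis at 410 or 162 events, treatment effect set so that power without pT stays near plan. 2,500 trials per cell.
- Set C: as A, with the planned strata and the entry limits on pT. Assumed 45% N+, 40% prior cisplatin and nodal HR 1.6; pT mix 25/50/25% in N+, 45/45/10% in N0 with cisplatin and 0/80/20% in N0 without. About 15,000 to 27,000 trials per cell.

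| Set | Assumed pT effect | All randomized, without → with pT | PD-L1 >=1%, without → with pT |
|---|---|---|---|
| A | 1.35 per level | 86.7 → 87.4% | 81.0 → 81.6% |
| A | 1.65 per level | 83.7 → 85.9% | 79.3 → 81.0% |
| A | 2.0 per level | 79.8 → 83.8% | 73.8 → 77.7% |
| B | none | 85.5 → 85.3% | 78.7 → 78.6% |
| B | pT3 1.25, pT4 1.5 | 86.3 → 86.8% | 80.4 → 80.4% |
| B | pT3 1.5, pT4 2.0 | 87.0 → 88.4% | 79.8 → 80.8% |
| B | pT3 1.8, pT4 3.0 | 86.3 → 89.7% | 82.0 → 84.5% |
| C | 1.35 per level | 84.6 → 85.4% | 80.1 → 80.6% |
| C | 1.65 per level | 82.3 → 84.4% | 78.1 → 79.9% |
| C | 2.0 per level | 79.0 → 82.8% | 74.1 → 77.5% |

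In set B the pT3 and pT4 hazard ratios are against pT0-2. The Monte Carlo standard error of the gain is 0.2 to 0.4 points in A and 0.1 to 0.2 in C. Up to 1.65 per level (pT4 against pT0-2: 1.65² = 2.7) the gain is at most 2.2 points. The middle case of C in all randomized is worth about 5% more events: from normal quantiles, ((2.241 + 1.011) / (2.241 + 0.927))² = 1.05, and 0.05 × 410 is about 20 events. In C the two tests disagreed on significance in 3 to 10% of trials. Type I error of the adjusted test in A was 2.2% and 2.7%, within simulation error of 2.5%.

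**3. pT as a further stratum.** This would give 3 × 2 × 2 × 3 = 36 cells in all randomized and 3 × 2 × 3 = 18 in PD-L1 >=1%. In set B the change in power was −3 to +2 points and −6 to −2 points respectively. That set carried PD-L1 as a stratum in both populations, twice the planned cells in PD-L1 >=1%, so the second range probably overstates the loss.

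**4. Chance imbalance.** Assume 20% pT4. The standard error of the arm difference is √(2 × 0.2 × 0.8 / n).

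- n = 350 per arm: 3.0 points; P(difference of 5 points or more, either direction) about 10%.
- n = 147 per arm: 4.7 points; about 28%.

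At an assumed pT4 HR of 2, a 5-point difference multiplies the observed hazard ratio by exp(0.05 × ln 2) = 1.035 or its inverse: for example 0.72 to 0.745, or 0.61 to 0.63.

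**The case against.** A log-rank test stratified by the randomization factors is standard and valid, and protocol and SAP agree on it. Randomization controls type I error whether or not pT is modelled, and chance pT imbalance is already part of the 2.5%. This stands in full.

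The size of the gain rests on inputs the documents do not give. Sets A and C lay pT heterogeneity over the plan's population-average curves, which pushes power without pT as low as 79.0% and 73.8%, away from the plan; their largest gains come from there. This also stands. Set B, held near the planned power, gives about 0 to 3.4 points.

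Entry rules partly tie pT to the strata: a node-negative subject without neo-adjuvant cisplatin must be pT3-pT4a. True, but set C builds this in and the gain remains.

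The SAP already has the supportive model, the baseline table and the subgroup. They would reveal an imbalance, but would not alter the confirmatory result.

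A reader might infer that the primary analysis is biased, that the trial is underpowered, or that chance imbalance could overturn the result. The documents support none of these: the test is valid, the stated power reproduces, and a 5-point imbalance in pT4 moves the hazard ratio by only 3 to 4% under the assumption above.

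**Conclusion.** The point holds as one of efficiency and precision, not as an error in the plan. The alpha-controlled DFS analysis omits a collected factor that the SAP treats as prognostic. Entering it as a covariate would add about 0 to 4 points of power in each co-primary population. The gain is about 2 points or less unless pT is strongly prognostic (around 2.0 per level, or pT4 against pT0-2 of about 3 or more), and the cost is 0.1 to 0.2 points if pT carries no information. All of these sizes depend on the assumed pT mix and effect. The change is still worth making because the possible loss is small and no extra subjects or data are needed.

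**What to change.** Amend Protocol 8.4.2.1 and SAP 7.5.1.1 before any efficacy unblinding. SAP 7.5.3 gives the DMC unblinded efficacy reports, so the change must come from staff who have not seen them.

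- Keep the IRT strata and the alpha spending.
- Name one primary procedure: the test of treatment and the hazard ratio from the stratified Cox model with treatment plus pT category (pT0-2, pT3, pT4). State the test statistic; set B used the Wald test. A covariate-adjusted log-rank test with robust variance is a different procedure and should not be treated as equivalent.
- Enter pT as a covariate, not as a further stratum, because extra cells could lower power in PD-L1 >=1%.
- Take pT from the pre-randomization resection pathology on the CRF, and fix in advance the category for a missing value.
- State that the hazard ratio is conditional on pT and that the boundary hazard ratios in Protocol Tables 8.1-1 and 8.1-2 and SAP Tables 5-1 and 5-2 are then approximate.
- Keep the present stratified log-rank test and treatment-only hazard ratio as the first sensitivity analysis.
- Do the same for OS (Protocol 8.4.2.2, SAP 7.5.2.1), including the boundary hazard ratios in Protocol 8.5 and SAP 5.1.

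The cost is wording; the covariate is already coded for the supportive model. The downside is a slightly different target (0.726 against 0.737 in the strongest all-randomized case of set C) and a primary analysis that depends on a CRF variable rather than on IRT factors alone.
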